8.6 Endpoints

8.6.1 Primary Endpoints

Part 1 (Phase 1):

Safety and tolerability of cePolyTregs as assessed by DLTs, defined as any related treatment-emergent adverse event (TEAE) with an NCI CTCAE 5.0 grade ≥ 3 which also represents a shift from baseline clinical status of ≥ 1 NCI CTCAE grade.

Part 2 (Phase 2a):

Efficacy of cePolyTregs compared with placebo/SOC, as assessed by time to recovery, defined as the first day during the 28 days after randomization on which a subject meets the criteria for category 0, 1, 2, 3, or 4 on the WHO severity scale for COVID-19 pulmonary syndrome.

Safety of cePolyTregs as assessed by the occurrence of related TEAEs with an NCI CTCAE 5.0 grade ≥ 3 .

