12 ADVERSE EVENTS

An AE is defined as any unfavorable and unintended sign (including an abnormal laboratory finding), symptom, or disease or any worsening of a pre-existing condition temporally associated with the use of a study drug, whether or not related to study drug. From signing the ICF to study drug administration, all SAEs and nonserious AEs related to protocol-mandated procedures will be recorded on the SAE/AE eCRF. All other untoward medical occurrences observed during screening, including exacerbation or changes in the medical and surgical history will be captured on the medical and surgical history eCRF.

An AE that occurs before the first administration of the study drug will be considered a pre-treatment AE. A TEAE is defined as any adverse event that was not present before the first administration of the study drug, or any event already present, that worsens in either severity or frequency, following exposure to the study drug. AEs that occur after treatment with IP or during the Safety Follow-up Period will be documented on the AE eCRF. The investigator will assess AE severity, the causality relationship of the AE to study drug, and will treat the subject as medically required to ensure the subject's safety.

AEs will be captured through the EOS Visit at Day 56 or the ET Visit. Reportable adverse events are defined based on timing of study drug administration, as follows:

- Treatment – Day 7: AEs grade 3+ that are not expected to occur in critically ill patients, per the discretion of the investigator.
- Treatment Day 8 – Day84/EOT: AEs grade 4+ that are not expected to occur in critically ill patients, per the discretion of the investigator.

Events expected in the critically ill and are being captured in the eCRF should not be reported as adverse events unless considered to be related to the study drug or unexpectedly severe or frequent per the discretion of the investigator. These include but are not limited to; need for vasoactive drugs or fluids for hypotension, decreased PaO₂/FiO₂, transient hypoxemia, need for renal replacement therapy, or worsening acute respiratory distress syndrome.

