12.6 Reporting Adverse Events

12.6.1 Reporting Procedures for Nonserious Adverse Events

The investigator is responsible for ensuring that all reportable AEs observed by the investigator or designee or reported by the subject are reported using the AE eCRF.

The investigator will assign the following AE attributes:

- AE diagnosis or syndrome(s), if known (if not known, signs or symptoms)
- Dates of onset and resolution (if resolved)
- Severity
- Causality relationship to study drug or study-related procedures
- Action taken
- Outcome

Follow-up of nonserious AEs will continue through the last day on the study and/or until a definitive outcome (e.g., resolved, resolved with sequelae, lost to follow-up) is achieved.

When a subject is withdrawn from the study because of a nonserious AE, the Sponsor and/or designee must be notified by email or phone within 48 hours.

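### Section 12 conflicts with itself and with the Part 2 primary safety endpoint on whether a related, unexpected grade 3 adverse event after Day 7 must be entered on the AE eCRF

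*Combined protocol and SAP*

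**What the plan says.** **Endpoint.** Section 8.6.1 and the synopsis give the Part 2 primary safety endpoint as "Safety of cePolyTregs as assessed by the occurrence of related TEAEs with an NCI CTCAE 5.0 grade" of 3 or higher. Neither place gives a time window. The TEAE definition in Section 12 and the analysis text in Sections 13.1 and 13.6 give none either.

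**General recording sentence.** Section 12 states: "AEs that occur after treatment with IP or during the Safety Follow-up Period will be documented on the AE eCRF". It carries no grade limit.

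**Reportability list.** Later in Section 12, reportable events are defined by period:
- from treatment to Day 7: "AEs grade 3+ that are not expected to occur in critically ill patients, per the discretion of the investigator";
- from Day 8 to Day 84: "AEs grade 4+ that are not expected to occur in critically ill patients, per the discretion of the investigator".

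**Relatedness exception.** The next paragraph concerns events that are expected in the critically ill. These "should not be reported as adverse events unless considered to be related to the study drug or unexpectedly severe or frequent".

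**eCRF duty.** For nonserious events, Section 12.6.1 makes the investigator responsible for ensuring that "all reportable AEs observed by the investigator or designee or reported by the subject are reported using the AE eCRF".

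**End of capture.** Section 12 also says "AEs will be captured through the EOS Visit at Day 56 or the ET Visit", while its own second bullet runs to "Day84/EOT: AEs grade 4+ that are not expected to occur in critically ill patients".

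**The concern.** An endpoint and the rule that collects its data should cover the same events. Here the endpoint threshold is grade 3 throughout, while the reportable threshold for unexpected events rises to grade 4 after Day 7. A site that follows the list can leave out events that belong in a primary endpoint. A site that follows the general recording sentence would enter them. With up to 12 centers, both practices could occur in one trial.

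The timing matters on the protocol's own account. Section 8.1.1 expects exposure to last about two weeks, so the threshold rises roughly midway through it. Section 12.5 sets a low bar for relatedness, since any possibility of a link is enough. Related grade 3 events in the second week or later are therefore plausible.

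If they are omitted, the tables by worst grade and relationship in Section 13.6 would mix a grade 3 threshold up to Day 7 with a grade 4 threshold afterwards. Nothing in the tables would show it.

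**Working it through.** The plan states no figure to reproduce. The check sets the rules side by side.

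**Step 1. Which related grade 3 events must be entered?** Each row is an event judged related, of exactly grade 3, with onset after dosing. All four rows meet the endpoint in Section 8.6.1.

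| Type of related grade 3 event | Must be entered to Day 7? | Must be entered Day 8 to 84? | Source |
|---|---|---|---|
| Expected in the critically ill | Yes | Yes | Exception in Section 12, which has no grade or day limit |
| Unexpected, SAE | Yes | Yes | Section 12.6.2, all SAEs whatever the cause |
| Unexpected, nonserious, on the AESI list | Yes | Yes | Section 12.2 (its arrhythmia and hypoxemia items apply only within 6 hours of exposure) |
| Unexpected, nonserious, not an AESI | Yes | **Not under the list; yes under the general recording sentence** | Section 12 list with 12.6.1, against the general sentence in Section 12 |

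The gap is the last row after Day 7. The result is odd: a late grade 3 event judged related is reportable if it was expected, but not if it was unexpected.

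**Step 2. Do other records close the gap?** Only in part.
- Section 14.7 requires progress notes to record severity and relationship for any adverse event, and says adverse events are entered in the database. It does not say whether that overrides the list.
- Section 13.6 grades laboratory values by CTCAE, but a graded value carries no relatedness judgement, which the endpoint needs.
- A separate SAP is promised in the synopsis and Section 13. It could define a window, but it could not restore events that were never entered.

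**Step 3. What is outside the gap?**
- *Part 1 escalation.* Section 8.8.1 bases these decisions on the 7-day DLT period. In that period unexpected events are reportable from grade 3, and related expected events are reportable too.
- *Stopping criteria on deaths and on related grade 4-5 TEAEs (Section 8.8.6).* Unexpected events of grade 4 or higher stay reportable to Day 84, and so do related expected events.

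**Step 4. Size.** The documents give no rate for related, unexpected, nonserious, non-AESI grade 3 events after Day 7, so no undercount can be calculated. The only arithmetic available is the weight of one subject: in a 50-subject arm, a subject whose only qualifying event is not entered lowers the observed rate by 1/50 = 2.0 percentage points. That is a unit of measure, not an estimate.

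**Step 5. End date.** The sentence placing the EOS Visit at Day 56 disagrees with the Day 84 bullet in the same section, with the AE assessment at Day 84 in the Schedule of Events, and with Section 8.1.5, which puts EOS on Day 84.

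**The case against.** The strongest reply is that the general recording sentence and Section 14.7 already require these events to be recorded, so nothing is lost. This stands in part. It rules out a stronger reading that a reader might infer, namely that Section 12 simply stops collecting grade 3 events after Day 7. The documents do not support that: they conflict, and SAEs, AESIs and related expected events remain reportable. But the reply does not remove the conflict. The list comes after the general sentence, it defines what is reportable, and Section 12.6.1 ties eCRF entry to that term.

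A second reply is that the gap is narrow. That is correct. An event must be related, unexpected, exactly grade 3, later than Day 7, and neither an SAE nor an AESI. SAEs include prolonged hospitalization and important medical events (Section 12.1). For events not covered by CTCAE, the fallback definition of grade 3 in Section 12.4 largely overlaps the SAE criteria. A reader might take the long span of the Day 8 to Day 84 threshold as a sign that much of the endpoint is lost. Calendar time says nothing about the number of events, and that inference should not be drawn.

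A third reply is that the analysis is descriptive, with no formal comparison (Section 13.1), and that the rule is the same in both arms. This limits the consequence. Even so, a descriptive endpoint consists of the recorded count, and an equal rule does not guarantee equal loss.

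Finally, the eCRF Completion Guidelines named in Section 12.6.2 may settle which sentence governs. They are not in the documents. If they do settle it, the protocol text would still need correcting.

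**Conclusion.** The point holds as an internal conflict with a narrow gap. Section 12 gives two answers on which adverse events go on the AE eCRF. Under one of them, a related, unexpected grade 3 event after Day 7 that is neither an SAE nor an AESI meets the Part 2 primary safety endpoint without having to be entered.

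This rests on reading the list and Section 12.6.1 literally, and on the exception for related events applying only to expected events, as it is worded. The text mismatch is certain. A practical undercount is possible, but it is not shown, its size is unknown and it may be small. No effect is claimed on Part 1 escalation decisions or on the stopping criteria for deaths and related grade 4-5 events. The conflict should be fixed because it touches a primary endpoint and events left out of the eCRF cannot be recovered at analysis.

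**What to change.** In Section 12:
1. Make every TEAE judged related and of grade 3 or higher reportable on the AE eCRF from dosing through the Day 84 EOS or ET Visit, whether or not it is expected in the critically ill.
2. Keep the reduced reporting for unrelated events.
3. Reconcile the general recording sentence with this rule, so that one statement governs eCRF entry.
4. Correct the wording that places the EOS Visit at Day 56.

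Carry the same rule into the eCRF Completion Guidelines.

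The cost is a wording change in Section 12 and the guidelines, and some additional AE forms at sites. No new visit, sample or assay is needed.

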8.6.2 Secondary Safety Endpoints

Part 1 (Phase 1):

RP2D of cePolyTregs as assessed by cumulative safety, tolerability, pharmacodynamic and biomarker changes associated with administration of cePolyTregs compared with placebo/SOC

Parts 1 and 2:

Safety and tolerability of cePolyTregs as assessed by:

- Type and frequency of TEAEs
- Type and frequency of treatment-emergent serious adverse events (TESAEs)
- Type and frequency of adverse events of special interest (AESIs) including infusion/hypersensitivity reactions, increase in SARS-CoV-2 viremia, and infections including pneumonia and those involving pathogens not anticipated in a COVID-19 setting
- Type and frequency of changes in clinical laboratory values, physical examinations, electrocardiograms (ECGs), and vital signs

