8.8.6 Study Discontinuation

The study may be stopped at the discretion of the Sponsor based on recommendations of the DSMB. The study may also be stopped pending DSMB evaluation of all available safety and PD data if any of the following occur:

- Any study drug-related death
- The occurrence of 3 deaths within 28 days post treatment in the first 5 subjects treated or, subsequent to the first 5 subjects, the observed mortality rate across the cumulative population of treated subjects exceeds the anticipated mortality rate of 50%
- Two CTCAE Grade 4 or 5 TEAEs that are deemed related to study drug
- An increase in the incidence of infections of special interest (pneumonia or infections involving pathogens not anticipated in a COVID-19 setting) beyond the expected background incidence

If the DSMB recommendation is to interrupt study dosing for all subjects or to pause enrollment, study dosing can be resumed, based on the recommendation of the DSMB, only after further review of all available safety data and applicable notifications of submission to appropriate regulatory agencies and institutional review committees, in line with country-specific regulations.

All deaths occurring during the study will be reviewed promptly by the DSMB as they occur. If at any point following enrollment of the first 5 subjects, the observed mortality rate across the cumulative population of treated subjects exceeds the anticipated mortality rate of 50%, the study will be halted.

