12.2 Adverse Events of Special Interest

To date, there have been no clinical studies using cePolyTregs, and nonclinical studies with autologous, homologous products have not demonstrated specific toxicities related to administration of adoptively transferred Tregs. Potential adverse events of interest in the COVID-19 setting based on the biology of cePolyTregs include infusion/hypersensitivity reactions and infections including pneumonia and those involving pathogens not anticipated in a COVID-19 setting; these clinical parameters will be closely monitored in the current study.

The following events are defined as AESIs that should be reported by completing the Adverse Event eCRF and AESI eCRFs within 24 hours of the site's awareness of them, even if they do not meet criteria for an SAE:

- Evidence of hypersensitivity or transfusion incompatibility (e.g. new rash, urticaria, new onset bronchospasm).
- Diagnostically or clinically confirmed respiratory infections that were not present before study drug infusion AND that require a treatment course with antimicrobial agents, operative management, or procedural drainage.
- Within 6 hours of IP exposure:
 - New ventricular tachycardia, ventricular fibrillation, or asystole or any cardiac arrhythmia requiring cardioversion.
 - Hypoxemia requiring an increase in FiO₂ of 0.2 or more and/or an increase in PEEP of 5 cm H₂O or more to maintain SpO₂ in the target range of 88–95%, for a sustained duration (>2 hours) and not associated with a care procedure.

- Pulmonary Embolism

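### Sections 12 and 12.2 give opposite reporting instructions for some adverse events of special interest, and some infections relevant to stopping fall under the Section 12 filter alone

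*Combined protocol and SAP*

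**What the plan says.** Section 12 defines reportable adverse events by time and grade. From treatment to Day 7 they are "AEs grade 3+ that are not expected to occur in critically ill patients, per the discretion of the investigator". From Day 8 to Day 84 they are "AEs grade 4+ that are not expected to occur in critically ill patients, per the discretion of the investigator". It then says that events expected in critical illness and already captured in the eCRF "should not be reported as adverse events unless considered to be related to the study drug or unexpectedly severe or frequent", at the investigator's discretion. The examples include decreased PaO2/FiO2, "transient hypoxemia, need for renal replacement therapy, or worsening acute respiratory distress syndrome". AESIs are not named as an exception to any of this. Section 12.6.1 makes the investigator responsible for entering reportable AEs, which is the term that Section 12 restricts.

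Section 12.2 sets a separate duty: "The following events are defined as AESIs that should be reported by completing the Adverse Event eCRF and AESI eCRFs within 24 hours" of the site becoming aware, whether or not the event is serious. Its list has no minimum grade and no expectedness test. It includes hypersensitivity signs such as new rash or urticaria, new respiratory infections that need treatment, and hypoxemia within 6 hours of infusion that lasts more than 2 hours.

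Section 8.6.2 makes the type and frequency of AESIs a secondary safety endpoint in both parts. It counts infections including pneumonia and those with pathogens not anticipated in COVID-19. Section 8.8.6 allows the study to be stopped for "An increase in the incidence of infections of special interest", defined as pneumonia or infections with such pathogens, above background. Neither section has a grade limit.

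**The concern.** An AESI list exists so that named risks are collected without first passing a test of severity, expectedness or causality. Section 8.2 describes infusion reactions and infections as class risks of this kind of product. If a site applies the general Section 12 definition to an event on the 12.2 list, the event enters the database only if it is severe enough and judged unexpected, or comes in by another route. With up to 12 centers, the AESI count could then reflect which rule each site followed as well as what happened to its subjects. The count of infections that the DSMB weighs under 8.8.6 has the same weakness.

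**Working it through.** The documents state no figure on this point, so the check is a comparison of the rules.

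**Step 1. What does each section waive?** Section 12.2 waives the SAE criteria and nothing else. Section 12 lifts its exemption for expected events when they are related or unexpectedly severe or frequent. It does not say that this also lifts the grade threshold. Neither section refers to the other.

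**Step 2. Put the same nonserious event through both rules.**

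| Event | Section 12 with 12.6.1 | Section 12.2 |
|---|---|---|
| New rash or urticaria below grade 3 | Not reportable: below the threshold at any time | Report within 24 hours |
| New treated respiratory infection, grade 3, after Day 7 | Not reportable: threshold is grade 4 | Report within 24 hours |
| New treated respiratory infection judged expected in critical illness | Not reportable, unless the exception for related or unexpectedly severe or frequent events is taken to apply | Report within 24 hours |
| Hypoxemia within 6 hours of infusion, lasting more than 2 hours | Overlaps the exempt decreased PaO2/FiO2 and worsening ARDS | Report within 24 hours |

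The first three rows are clear conflicts. The fourth is an overlap: because the event must last more than 2 hours, it is not the transient hypoxemia on the exempt list.

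**Step 3. Follow the infections that matter for stopping.** The opening of 12.2 mentions infections with unanticipated pathogens as events to watch. The list that carries the reporting duty names only respiratory infections. A nonserious, non-respiratory infection with an unanticipated pathogen therefore has no AESI reporting duty, and only the Section 12 filter applies. Such an infection may pass the expectedness test, but the grade threshold remains. It belongs in the 8.6.2 endpoint and the 8.8.6 criterion, yet can go unrecorded as an AE at a site that follows every section.

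**Step 4. Can the loss be sized?** If 12.2 is followed, none of its listed AESIs is lost through this filter. If Section 12 is applied to them, the share lost is 1 − u × [w × g3 + (1 − w) × g4]. Here w is the share with onset by Day 7, g3 and g4 are the shares at grade 3 or higher and grade 4 or higher, and u is the share judged not expected. The documents give none of these. Purely assumed ranges (w 0.25 to 0.75, g3 0.5 to 0.9, g4 0.1 to 0.4, u 0.25 to 1.0) give these extremes:

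- lowest: 1 − 1.0 × (0.75 × 0.9 + 0.25 × 0.4) = 1 − 0.775 = 22.5%
- highest: 1 − 0.25 × (0.25 × 0.5 + 0.75 × 0.1) = 1 − 0.05 = 95%

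The formula leaves out the SAE route and the exception for related events, both of which reduce the loss. It also applies only to sites that read the rules this way, and that number is unknown. The spread shows that no useful size can be given; it is not an estimate.

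**The case against.** The strongest reply is that 12.2 sits inside Section 12, is the more specific rule and has its own eCRF, so a careful site will follow it and lose no listed AESI. That is a fair reading, but the protocol does not state it. By waiving only seriousness, 12.2 leaves room for the view that the other limits still apply.

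Other routes also recover events:

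- All SAEs are reported within 24 hours whatever their cause (12.6.2), including those that prolong hospitalization (12.1). Some treated infections in ventilated patients would qualify. Nonserious events are not helped.
- Section 12 also states that "AEs that occur after treatment with IP or during the Safety Follow-up Period will be documented on the AE eCRF", with no grade limit. The reportable-event definition that follows, and 12.6.1, narrow this again.
- The exemption covers only events captured elsewhere in the eCRF. Ventilator settings are recorded daily while a subject is ventilated (11.8), and antibiotics and ventilator changes are recorded too (11.14). These data could support a reconstruction, but they are not AESI records.
- Section 12.5 sets a low bar for calling an event related, so much hypoxemia soon after infusion would escape the exemption. That weakens the hypoxemia example. It does not clearly remove the grade threshold for rash, urticaria or later infections.

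The infection criterion in 8.8.6 is discretionary, draws on all available safety and PD data, and names no eCRF source. The filter therefore does not disable it. The DSMB can still weigh only what has been recorded, and Step 3 stands even where 12.2 is read as governing.

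**Conclusion.** The conflict is real and should be resolved. Sections 12 and 12.2 give opposite instructions for nonserious AESIs that fall below the grade thresholds or are judged expected, and the protocol does not say which prevails. There is also a gap: nonserious, non-respiratory infections with unanticipated pathogens count in 8.6.2 and 8.8.6 but can be filtered out by Section 12 under any reading. Both conclusions rest on the text alone.

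Three stronger inferences are not supported. A reader might infer that Section 12 removes AESIs from the database; it does not, because 12.2 is an independent duty to report them. A reader might infer that most AESIs would be lost; the documents give no rates, onset times or grade distribution, and the answer depends on how sites resolve the conflict. A reader might infer a loss of power to compare AESI rates between arms; no such test is planned. Section 13.6 summarizes AESIs by subject incidence, and Section 13.1 rules out formal comparison between arms even for the primary safety endpoint.

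**What to change.** Add one sentence to Section 12 and repeat it in 12.2: AESIs listed in 12.2, and all infections counted under 8.6.2 and 8.8.6, are recorded on the AE and AESI eCRFs at any grade, whether or not expected or judged related; the Section 12 grade thresholds and list of expected events do not apply to them. Naming the infections matters, because a sentence limited to the 12.2 list would leave the non-respiratory ones filtered.

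Reconcile the end of AE capture at the same time. Section 12 places the EOS visit at Day 56 in one sentence and runs reportable events to Day 84 in the next, so the new duty needs one stated end date. Carry both changes into the eCRF completion guidelines.

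The cost is one sentence in two places, a date correction, and some extra AE entries per site, most of which 12.2 already asks for.
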